2 PROCEDURES

The study for an individual patient will generally consist of the following periods:

- Screening/Qualification:
- Qualification of Group 1 and 2 patients (participated in ISIS 304801-CS6 or ISIS 304801-CS16 index study): A qualification period of up to 2 weeks (unless approved by the Sponsor).
- Screening and Qualification of Group 3 patients (did not participate in an index study): An up to 8-week screening and qualification period, including a diet stabilization period of at least 6 weeks.
- A 52-week treatment period during which volanesorsen will be administered as a once weekly SC injection
- Option to participate in an extended treatment period (up to an additional 52 weeks)
- A 13-week post-treatment evaluation period

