	104	722	674 to 743
	117	813	744 to 858
	130 (France)	904	859 to 949
Abdominal Pain			
	m	$n \times 7 + 1$	$mx7+3 \text{ to } mx7-3,$ $m = -1, -2, \dots$
	...		
	-2	-13	-11 to -17
	-1	-6	-4 to -10
	1	1	1 to -3
	2	8	5 to 11

	3	15	12 to 18
	n	(n-1) × 7+1	(n-1) × 7-2 to (n-1) × 7+4
	...		
MRI			
	Screening	NA	≤ 14
	52	358	298 to 418
Quality of Life Assessments (EQ-5D, SF-36)			
	1	1	1
	13	85	55 to 115
	26	176	146 to 206
	52	358	328 to 404
	65	449	405 to 479
	78 (France)	540	496 to 570
	117 (France)	813	769 to 843
	130 (France)	904	860 to 934

Note: Regarding lipid measurements for efficacy analyses, mapped observed assessments defined in this table will be derived further. The derivations for baselines are described in [section 3.2.3](#). The derivations for Month 3, 6 and 12 are described in [section 3.3.1](#).

Non-efficacy by visit assessments will be summarized using the visit labels provided in the data. Multiple results with the same visit label will be averaged.

Unscheduled results and data from local labs will not be included in the by visit summaries but will be used in the determination of baseline, in the laboratory abnormality, stopping rule, and platelets reduction analyses presented in data listings.

Unscheduled results from the central lab will be used in the determination of baseline, laboratory abnormality summaries, and shift from **safety baseline** to worst post-baseline, and platelets reduction analyses only, and presented in data listings. Local lab data will be only used in platelet analyses (including by visit summaries, abnormality summary, shift from Baseline to worst post-baseline, reduction analyses), and presented in data listings.

Summary tables and figures will NOT be presented by the treatment group in each index study (ISIS 304801-CS6 or ISIS 304801-CS16) and the newly enrolled patients as a separate group per protocol. Per Sponsor decision, most summary tables and figures will be presented in the following groups, i.e. Treatment naive group, CS6-Volanesorsen, CS16-Volanesorsen, and Overall, if applicable.

Note: “Treatment naive group” for most tables and figures is a combined group of subjects including CS7-New, CS6-Placebo and CS16-Placebo. When the summary is based on **Index Study Baseline**, “Treatment naive group” is a combined group of subjects including CS6-Placebo and CS16-Placebo.

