3.2.3 Baselines and Other Definition

Baselines for fasting lipid measurement:

Definitions of baselines, including the **Index Study Baseline** (for Group 1 and Group 2 only) and the **Open-label Study Baseline** (for Group 1, 2, and 3), are given below for the purposes of the final analysis.

- **Index Study Baseline for Group 1 and 2** is defined as the average of Index Study Day 1 pre-dose assessment and the last measurement prior to Index Study Day 1 pre-dose assessment. If one of the two measurements is missing, then the other measurement will be assigned as the baseline value. If both are missing, then the baseline will be set as missing.
- **Open-label Study Baseline for Group 1, 2 and 3** is defined as the average of open-label Day 1 pre-dose assessment and the last measurement prior to open-label Day 1. If one of the two measurements is missing, then the other measurement will be assigned as the baseline value. If both are missing, then the baseline will be set as missing.

Baselines for QOL (EQ-5D, SF-36):

1. **Index Study Baseline for Group 1** is defined as the last non-missing assessment on Week 1 of treatment, volanesorsen or Placebo, in index studies.
2. **Open-label Study Baseline for Group 1, 2 and 3** is defined as the last non-missing assessment on Week 1 in this Open-label study.

Baselines for patient reported abdominal pain:

1. The average of maximum intensity:
2. **Index Study Baseline for Group 1** is defined as the average of maximum intensity during the screening period and Week 1 in index studies.
3. **Open-label Study Baseline for Group 1, 2 and 3** is defined as the average of maximum intensity within 4 weeks (including week 1) prior to Day 1 of treatment in this open-label study.
4. The worst of maximum intensity:
5. **Index Study Baseline for Group 1** is defined as the worst of maximum intensity during the screening period and Week 1 in index studies.
6. **Open-label Study Baseline for Group 1, 2 and 3** is defined as the worst of maximum intensity within 4 weeks (including week 1) prior to Day 1 of treatment in this open-label study.

Safety Baseline for Platelet count: is defined as the average of all available measurements, including central lab measurements and local lab measurements, prior to Day 1 of volanesorsen, i.e.

1. For subjects in Group 1 and 2 who were treated with volanesorsen in the index study, it is all available measurements prior to Day 1 of treatment in index study

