3.3.5 Frequency and severity of patient reported abdominal pain

The maximum intensity of abdominal pain related to disease will be collected on the FCS symptom questionnaire and reported by patients weekly on Bracket electronic patient reported outcomes (ePRO). The average maximum intensity of patient reported abdominal pain score during the on-treatment period will be summarized. The patients' reported results will be mapped to each visit week based on the visit window specified in [section 3.2.1](#). If patients have multiple results within a visit window, the worst score will be used for summary and analysis. The results at Week 1 will not be included in the on-treatment period, since the results are reported retrospectively to collect the symptoms of patients during the past week. The missing data will be imputed by using Next Observation Carried Back (NOCB) if there is a subsequent score available. Otherwise, the missing data after the last available score of each patient will not be imputed.

Two (2) types of summary tables will be provided in the subset of FAS patients who reported any abdominal pain (pain score > 0) during the screening period and Week 1. Baselines are defined in the [section 3.2.3](#).

1. Change from both **Index Study Baseline** and **Open-label Study Baseline** in the average of maximum intensity of patient reported abdominal pain will be summarized.
2. Change from both **Index Study Baseline** and **Open-label Study Baseline** in the worst weekly patient reported maximum intensity abdominal pain score during the treatment period will be summarized.
3. The same method described above will be used to impute the missing data in exploratory analyses.

The abdominal pain score in each week will be categorized to no pain (pain score: 0), mild (pain score: 1–3), moderate (pain score: 4–6), or severe (pain score: 7–10). A summary by the category will also be provided for safety set overall, and for CS6 subjects who roll-over to CS7. Other information of the abdominal pain questionnaires will be listed in a patient data listing.

Summary table and figure for abdominal pain intensity change for patients with pain at baseline in CS6 subjects who roll-over to CS7 will be generated.

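### The change in worst abdominal-pain score sets a short-baseline maximum against one maximum over the whole treatment period, so with no drug effect it rises with each patient's follow-up

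*SAP*

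**What the plan says.** Section 3.3.5 of the SAP plans two changes for the weekly abdominal-pain score: one in average intensity, and one "in the worst weekly patient reported maximum intensity abdominal pain score during the treatment period will be summarized". Both are given from two baselines and in the "subset of FAS patients who reported any abdominal pain (pain score > 0) during the screening period and Week 1".

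Section 3.2.3 defines the worst-score baselines. The open-label one "is defined as the worst of maximum intensity within 4 weeks (including week 1) prior to Day 1 of treatment in this open-label study". The index one "is defined as the worst of maximum intensity during the screening period and Week 1 in index studies"; this document does not give the length of the index screening period.

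On the on-treatment side, section 3.3.5 says: "The results at Week 1 will not be included in the on-treatment period". A gap before a later report is filled with that later score, and nothing is imputed after a patient's last report. Section 2 gives 52 weeks of treatment with an optional extension of up to 52 more. Section 3.2.1 says that "most summary tables and figures will be presented in the following groups, i.e. Treatment naive group, CS6-Volanesorsen, CS16-Volanesorsen, and Overall, if applicable". Section 3.3.5 also plans a table and figure of "abdominal pain intensity change for patients with pain at baseline in CS6 subjects who roll-over to CS7".

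**The concern.** The two ends of the change are maxima over different numbers of weeks, and the longer end varies between patients. The baseline maximum is fixed once treatment starts, while the on-treatment maximum can only hold or climb with each further report. Carrying a later score back adds no new maximum, so the number of chances to record a high score is set by the patient's own follow-up. Section 3.3.5 neither fixes a common period nor matches the lengths.

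Abdominal pain is a listed efficacy endpoint (section 1.4.1), and a change from baseline invites reading as benefit or harm. A group with more early stopping would look better on this measure than one that stayed on treatment, even if weekly pain were identical.

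A second effect pulls the other way. Keeping only patients with a pain score above 0 in weeks that include the baseline weeks raises the average baseline worst score, and later scores then tend to fall back (regression to the mean). The observed change mixes both effects with any drug effect.

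**Working it through.** The SAP states no figure for this quantity, so there is none to reproduce. The direction follows from the definitions; the size needs assumptions.

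**Inputs from the SAP**
- Weekly reports (3.3.5).
- Open-label baseline of about 4 scores (3.2.3).
- Week 1 excluded on treatment (3.3.5), so 52 - 1 = 51 scores to Week 52 and 104 - 1 = 103 if the full extension is counted.
- Group 3 screening of up to 8 weeks (section 2). With Week 1 this is up to 8 + 1 = 9 selection weeks, assuming weekly reports throughout.

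**Assumptions (not in the SAP), with no drug effect**
- Mean weekly probability of pain p = 2, 5, 10, 20 or 30%, either equal across patients or beta-distributed (a + b = 2).
- Severity either drawn afresh each week from 1 to 8, or patient-specific (typical level 1 to 8, weekly scores within 1 point).
- Weeks independent given the patient. This makes 5 x 2 x 2 = 20 patterns.

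**Formulas**
- Given a patient, P(max of L scores <= m) = (1 - p x P(severity > m))^L, and E[max_L] is the sum over m = 0 to 9 of one minus that probability.
- All patients: change = E[max_L] - E[max_4].
- Selected on s weeks that contain the baseline weeks: change = E[(max_L - max_4) x 1(max_s > 0)] / P(max_s > 0).

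**One pattern in full** (p = 10% for everyone, fresh severity 1 to 8)
- E[max_4] = 1.62, E[max_12] = 3.76, E[max_51] = 6.91.
- All patients, 51 scores: 6.91 - 1.62 = +5.29.
- Selected on the same 4 weeks: P(max_4 > 0) = 1 - 0.9^4 = 0.344, so the mean baseline is 1.62 / 0.344 = 4.71. The change is 6.91 - 4.71 = +2.2 with 51 scores but 3.76 - 4.71 = -0.95 with 12.
- Selected on 9 weeks: 1 - 0.9^9 = 0.613, so the mean baseline is 1.62 / 0.613 = 2.64. The change is 6.91 - 2.64 = +4.27 with 51 scores.

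**Range over the 20 patterns, 4-week baseline (points)**

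| On-treatment scores | Selected on same 4 weeks | Selected on 9 weeks | All patients |
|---|---|---|---|
| 4 (equal length) | -4.20 to -0.98 | -1.77 to -0.15 | 0 |
| 12 | -3.57 to +1.25 (11 of 20 below 0) | -1.14 to +2.32 (4 of 20) | +0.18 to +2.62 |
| 51 | -1.50 to +2.69 (2 of 20) | +0.93 to +4.27 (0 of 20) | +0.44 to +5.29 |
| 103 | -0.23 to +2.99 (1 of 20) | +1.51 to +4.98 (0 of 20) | +0.57 to +6.06 |

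From 12 to 51 scores the no-effect change rises in all 20 patterns, by 0.39 to 3.34 points. The first row isolates regression to the mean: with equal lengths it is all that remains in the subset, and it is zero in all patients.

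For the index baseline, if it holds 9 scores and selection uses the same 9 weeks, the change with 51 scores is -1.5 to +2.0.

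**Sensitivity to week-to-week correlation.** Under a different model (rounded 0 to 10 score, patient random effect, serial correlation 0 to 0.8, 4-week baseline, selected on the baseline weeks) the change is +0.4 to +0.7 with 12 scores, +1.9 to +2.3 with 51 and +2.7 to +2.9 with 103. The rise with follow-up remains.

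**The case against.** The strongest reply is that little rests on this table. Section 1.3 states no formal hypothesis, section 3.1 evaluates the study by summary tables, and there is no control arm. The SAP already holds pain summaries without the window-length problem: the average-intensity change, the weekly categories in the safety set, the 13-week windows of section 3.3 and, most directly, the yearly rate of moderate or severe pain in section 3.3.9. That rate is divided by on-treatment duration and covers the whole FAS. This stands, and it limits the severity. It does not make the worst-score change interpretable.

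The size is also model-dependent. At 10 to 30% pain weeks and 51 scores, selected on the baseline weeks, the change is +2.0 to +2.7 with fresh severity but +0.5 to +0.8 with patient-specific severity. With a severity distribution declining over 1 to 10 and pain frequency varying between patients, it is +3.4 to +3.8. That stands too; no single figure should be quoted.

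A reader might infer that the table will show a false improvement. The SAP does not support that as a general statement. Negative no-effect values at 51 scores appear only with very rare pain (2%, equal across patients) and selection on exactly the baseline weeks. The stated selection covers screening plus Week 1, which for Group 3 can be about 9 weeks, and then none of the 20 patterns is below 0.

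A reader might also take 103 scores as settled. Section 2 lists the treatment period and the extended treatment period separately, so whether the extension counts is open. If the on-treatment period of section 3.5 (last dose plus 28 days) is meant, the count to Week 52 is about 51 + 4 = 55.

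**Conclusion.** The point holds for the worst-score change only. Its no-effect value rises with each patient's follow-up; this follows from the definitions and needs no pain model. Patients or groups with different follow-up therefore cannot be compared on it, and neither its sign nor its size can be read alone as a drug effect.

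The size rests on the assumed patterns and on which weeks define the pain subset. That the baseline is short is established for the open-label baseline (4 weeks); the index length is not given. Regression to the mean in the subset applies where the selection weeks include the baseline weeks: for the index baseline, for Group 3, and for the CS6 rollover table if change is taken from the baseline used for selection. For other rollover patients against the open-label baseline, the SAP does not settle the overlap.

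A reader might conclude that the pain results as a whole are unreliable. That goes too far, given the summaries without this artefact. Severity is minor to moderate.

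**What to change.** In section 3.3.5, base the worst-score change on on-treatment windows with the same number of weeks as the baseline used. For the open-label baseline, this could be the per-patient mean of the worst score over complete 4-week blocks (51 scores give 12 complete blocks, with 3 scores left over). For the index baseline, use blocks of the patient's actual number of index baseline weeks. Each block need not be tabulated.

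Present this change in all FAS patients with a baseline, with the pain subset as supportive. Both parts are needed. Equal blocks alone still leave -4.2 to -1.0 points in a subset selected on the same 4 weeks (-1.8 to -0.2 if selected on 9). All patients without equal blocks still give +0.4 to +5.3 with 51 scores.

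The planned whole-period worst score may stay as a description, labelled as dependent on follow-up and not used to interpret change. It also keeps scores from incomplete last blocks in view.

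The cost is SAP wording, some programming and extra table rows; no new data are needed. Patients without a complete block do not contribute to the block mean, so their number should be shown.

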3.3.6 Percent change and change from baseline in other fasting lipid measurements

Percent change and absolute change from the **Open-label Study Baseline** at Month 3, Month 6, and Month 12 in this open label study, and percent change and absolute change from the **Index Study Baseline** in other fasting lipid measurements including total cholesterol, non-HDL-C, apoB, HDL-C, apolipoprotein A-1 (apoA-1), VLDL-C, and LDL-C at index study Month 3, Month 6, and Month, and the open label study Month 3, Month 6, and Month 12 will be summarized. For patients enrolled to extended treatment period, percent change and absolute change from the **Open-label Study Baseline** and percent change and absolute change from the **Index Study Baseline** in fasting TG at Week 64, 76, 90, and 104 will also be summarized. A descriptive summary of these measurements over time will also be conducted overall and by age group (<65 years vs. ≥65 years).

3.3.7 Percent change and change from baseline in fasting total apoC-III

Percent change and absolute change from the **Open-label Study Baseline** at Month 3, Month 6, and Month 12 in this open label study and percent change and absolute change from the **Index Study Baseline** in fasting total apoC-III at index study Month 3, Month 6, and Month, and the open label study Month 3, Month 6, and Month 12 will be summarized. For patients enrolled to extended treatment period, percent change and absolute change from the **Open-label Study Baseline** and percent change and absolute change from the **Index Study Baseline** in fasting TG at Week 64, 76, 90, and 104 will also be summarized. A descriptive summary of fasting total apoC-III over time will also be conducted.

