1.1 Study Overview

This is an open-label study of:

Group 1: ISIS 304801-CS6 (index study) roll over FCS patients

Group 2: ISIS 304801-CS16 (index study) roll over FCS patients

Group 3: FCS patients who did not participate in the ISIS 304801-CS6 or ISIS 304801-CS16 index studies.

Up to approximately 70 patients will receive 300 mg once weekly volanesorsen for 52 weeks in the CS7 study.

Following the Week 52 visit, patients will have the option of participating in an expanded access program or continuing dosing for up to an additional 52 weeks until an expanded access program is approved and available in their country. Patients not participating in an expanded access program will enter a 13-week post-treatment evaluation period.

There is no primary efficacy endpoint. Both efficacy endpoints and safety endpoints will be summarized to evaluate the safety and efficacy of extended dosing with volanesorsen sodium 300 mg in patients with FCS.

Groups 1 and 2 (Qualification): During the qualification period, the eligibility of the patient to enroll in the open-label study will be determined. Final assessments from the ISIS 304801-CS6 or ISIS 304801-CS16 studies may be used for qualification. A period of up to 2 weeks after completion of the ISIS 304801-CS6 or ISIS 304801-CS16 index studies (unless approved by the Sponsor) is given to complete qualification. Qualified patients will retain the unique patient identification number that was assigned to them during the ISIS 304801-CS6 or ISIS 304801-CS16 index studies.

Group 3 (Screening and Qualification): At the time of consent, the patient will be considered enrolled into the study and will be assigned a unique screening number before any study procedures, including screening procedures, are performed.

Patients will be enrolled into the treatment phase of the study after all Screening (Group 3) and qualification assessments have been completed and after the Investigator has verified that they are eligible per criteria in protocol Sections 5.1 and 5.2. No patient may begin treatment prior to enrollment.

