1.2 Objectives

To evaluate the safety and efficacy of dosing and extended dosing with ISIS 304801 (volanesorsen sodium 300 mg) in patients with FCS.

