1.4.1 Efficacy Endpoints

- Percent change and absolute change from baseline in fasting TG,
- Frequency and severity of patient reported abdominal pain during the on-treatment period,
- Percent change and change from baseline in other fasting lipid measurements including total cholesterol, non-HDL-C, apoB, HDL-C, apolipoprotein A-1 (apoA-1), VLDL-C, and LDL-C,
- Percent change from baseline in fasting total apolipoprotein C-III,
- Change from baseline in Quality of Life (QOL) questionnaires (EQ-5D, SF-36),
- Independently adjudicated acute pancreatitis event rate,
- Frequency of other symptoms: eruptive xanthoma, lipemia retinalis.

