2.1.3 Extended Treatment Period

Patients will have the option of continuing treatment for up to an additional 52 weeks until an expanded access program is approved and available in their country.

During the extended treatment period, patients will report to the study center for clinic visits during Weeks 54-104 (see Schedule of Procedures in Appendix A of the protocol). Study Drug will be administered once weekly unless the patient is on a biweekly treatment schedule for safety reasons. Collection and measurement of vital signs, clinical laboratory parameters (including hematology, serum chemistry, and urinalysis), AEs, concomitant medication/procedure information, lipid panel, volanesorsen plasma concentrations, IM testing, ECGs, and physical examinations will be performed according to the Schedule of Procedures in Appendix A. Adverse events at the injection site should

be collected as adverse events. Dietary counseling will be reinforced at intervals throughout the extended treatment period. All blood and urine samples should be collected prior to volanesorsen administration. Blood sampling at Weeks 53, 54, 55, 56, 57, 58, 59, 60, 61, 62, 63, 65, 66, 67, 68, 69, 70, 71, 72, 73, 74, 75, 77, 78, 79, 80, 81, 82, 83, 84, 85, 86, 87, 88, 89, 91, 92, 93, 94, 95, 96, 97, 98, 99, 100, 101, 102, and 103 may be conducted by a home healthcare nurse. Approval for study procedures to be conducted by a home healthcare nurse on other outpatient visit days will require prior approval by the Sponsor. Patients must be fasted prior to drawing all blood samples and samples drawn locally should also be sent to the central laboratory for analysis whenever possible. Treatment instructions and training will be provided to the patient where applicable.

2.1.4 *Pharmacokinetic (PK) Subgroup*

A subgroup of patients will participate in an extended PK collection. Patients in this subgroup will have more frequent PK sampling over a 24-hour period following the first dose on Study Day 1 in order to evaluate the plasma PK parameters of volanesorsen. Patients in this subgroup will have an additional visit to the clinic, or by a home healthcare nurse, on Day 2 to collect a 24-hour post-dose blood draw after dosing on Day 1. The detailed PK sampling schedules are outlined in Appendix C of the protocol.

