3 ANALYSIS PLAN

3.1 Statistical Design Summary

This is a multi-center open-label study of:

Group 1: ISIS 304801-CS6 (index study) roll over FCS patients

Group 2: ISIS 304801-CS16 (index study) roll over FCS patients

Group 3: FCS patients who did not participate in the ISIS 304801-CS6 or ISIS 304801-CS16 index studies.

Group 1 and Group 2 patients who complete one of the index studies and who are qualified plus Group 3 patients who are screened and qualified will be enrolled to this open-label study. The safety and efficacy of extended dosing with volanesorsen in patients with FCS will be evaluated by summary tables rather than hypothesis tests. Missing data will not be imputed.

3.1.2 *Sample Size Consideration*

No sample size calculations were performed as this is an open-label extension study.

3.1.3 *Planned Interim Analysis*

An interim analysis may be conducted after the last patient's Week 13 visit of the open-label study or after the database of the ISIS 304801-CS6 and ISIS 304801-CS16 index studies are locked and unblinded.

Planned summaries and patient data listings for disposition, demographic, efficacy and safety will be included in this interim analysis.

Additional interim analyses will be performed to support regulatory filing activities.

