3.3.2 Percent change and absolute change from baseline in fasting TG

The Month 3 analysis time point is at the end of Month 3 where the value is defined as the average of Week 12 (Day 78) and Week 13 (Day 85) fasting assessments. If one visit is missing, then the other visit will be used as the 3-month endpoint. If both visits are missing, then the 3-month endpoint will be set as missing.

The Month 6 analysis time point is at the end of Month 6 where the value is defined as the average of Week 25 (Day 169) and Week 26 (Day 176) fasting assessments. If one visit is missing, then the other visit will be used as the 6-month endpoint. If both visits are missing, then the 6-month endpoint will be set as missing.

The Month 12 analysis time point is at the end of Month 12 where the value defined as the average of Week 50 (Day 344) and Week 52 (Day 358) fasting assessments. If one visit is missing, then the other visit will be used as the 12-month endpoint. If both visits are missing, then the 12-month endpoint will be set as missing.

Percent change and absolute change from the **Open-label Study Baseline** at Month 3, Month 6, and Month 12 in this open label study, and percent change and absolute change from the **Index Study Baseline** in fasting TG at index study Month 3, Month 6, and Month 12, and the open label study Month 3, Month 6, and Month 12 will be summarized. For patients enrolled to extended treatment period, percent change and absolute change from the **Open-label Study Baseline** and percent change and absolute change from the **Index Study Baseline** in fasting TG at Week 64, 76, 90, and 104 will also be summarized.

These analyses will be repeated using on-treatment period data, which is defined as the last dose date of study medication + 28 days.

A descriptive summary of TG over time will be conducted overall and by age group (<65 years vs. ≥ 65 years). A descriptive summary of TG over time during on-treatment period will also be conducted overall.

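### Sections 3.3.6 and 3.3.7 name fasting TG for Weeks 64–104 instead of their own measures, and no Month 3–12 summary is planned for the extension cohort

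*SAP*

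**What the plan says.** The objective in SAP Section 1.2 covers both periods: "To evaluate the safety and efficacy of dosing and extended dosing with ISIS 304801". Section 1.4.1 lists two endpoints that matter here beside TG. One is "Percent change and change from baseline in other fasting lipid measurements including total cholesterol, non-HDL-C, apoB, HDL-C", continuing with apoA-1, VLDL-C and LDL-C. The other is "Percent change from baseline in fasting total apolipoprotein C-III".

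Sections 3.3.2 (TG), 3.3.6 (other lipids) and 3.3.7 (apoC-III) share one structure. Each plans percent and absolute change at Months 3, 6 and 12 for its own measures. Each then adds a sentence for the extension that opens "For patients enrolled to extended treatment period, percent change and absolute change from the" and refers to both baselines. In all three sections that sentence ends with change "in fasting TG at Week 64, 76, 90, and 104 will also be summarized". Sections 3.3.6 and 3.3.7 also plan a descriptive summary of their own measures over time and set no last visit.

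On who contributes: Section 3.3 places efficacy analyses in the FAS. Entry to the extension is voluntary and tied to local access (Section 2.1.3): "Patients will have the option of continuing treatment for up to an additional 52 weeks until an expanded access program is approved and available in" the patient's country. Section 3.1 does not impute missing data.

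**The concern.** Section 3.3.2 is right to name TG. Sections 3.3.6 and 3.3.7 are not, because neither concerns TG. A programmer who follows the text would produce the TG extension table three times and no extension table of change for apoC-III, apoB, LDL-C and the rest. Section 1 requires departures from the final plan to be justified and reported, so silently programming what was probably meant is not a clean remedy.

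The second issue is the cohort. Section 3.3 plans one display by visit window in which TG at Month 12 is followed by TG at Weeks 64, 76, 90 and 104. A reader will look down that column to judge whether the effect lasts. Between Month 12 and Week 64 the patients change as well as the time. If those who continue differ in response from those who do not, part of any apparent gain or loss comes from who is left.

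**Working it through.** The plan gives no figure to reproduce. Section 3.1 states: "No sample size calculations were performed as this is an open-label extension study". The check is a comparison of text, followed by one formula to show what the cohort issue depends on.

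**Step 1: which measures have a specified change at which visits.** Section 1.4 lists nine fasting measures: TG, total cholesterol, non-HDL-C, apoB, HDL-C, apoA-1, VLDL-C, LDL-C and apoC-III.

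| Section | Own measures | Months 3–12 names | Weeks 64–104 names |
|---|---|---|---|
| 3.3.2 | TG (1) | TG | TG |
| 3.3.6 | other lipids (7) | the 7 | TG |
| 3.3.7 | apoC-III (1) | apoC-III | TG |

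Measures without a specified change at Weeks 64–104: 7 + 1 = 8 of 9. The data should be available. Section 2.1.3 keeps the lipid panel in the extended period, and the fasting-lipid windows in Section 3.2.1 include Weeks 64, 76, 90, 104 and 117. The fault lies in the analysis instruction alone.

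**Step 2: who contributes to each time point.**
- Months 3–12: FAS patients with a value at the visit. Section 2.1.2 encourages patients who stop treatment early to attend the landmark visits up to Weeks 50 and 52, and Section 3.2.1 maps those values to analysis visits. FAS Month 12 can therefore include off-treatment values.
- Weeks 64–104: only patients who entered the extension, and at each visit only those with a value. Section 2.1.5 allows for early termination of the extension.
- No section summarises Months 3–12 for the extension patients alone.
- Section 3.3.2 repeats the TG analyses on on-treatment data. Sections 3.3.6 and 3.3.7 plan no such repeat.

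**Step 3: what a change of cohort can do.** Let f be the share of Month 12 patients who continue. Let C and N be the Month 12 mean percent change in continuers and non-continuers, and D = N − C. Suppose that no patient's value changes after Month 12 and that all continuers are seen at Week 64.

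- Month 12, all patients: f × C + (1 − f) × N
- Week 64, extension patients: C
- Apparent shift: f × C + (1 − f) × N − C = (1 − f) × D

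The document gives neither f nor D, so the values below are assumptions. Patient counts use the ceiling in Section 1.1, about 70.

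| f (patients of 70) | D = 0 | D = 10 | D = 20 | D = 30 |
|---|---|---|---|---|
| 0.5 (35) | 0 | 5 | 10 | 15 |
| 0.7 (49) | 0 | 3 | 6 | 9 |
| 0.9 (63) | 0 | 1 | 2 | 3 |

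Entries are percentage points. For example, f = 0.7 and D = 20 gives 0.3 × 20 = 6. A negative D reverses the sign, so that continuers would appear to lose effect.

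**The case against.** The strongest reply is that the analyte error is a visible carry-over and leaves less of a gap than it seems. The headings and surrounding sentences of 3.3.6 and 3.3.7 show what was meant. Section 3.3 maps fasting-lipid visits to the windows in 3.2.1, which run past Week 104. Both sections plan over-time summaries with no visit limit, and by-patient listings carry all efficacy results. Section 3.3.4 also plots percent change in all nine measures against the number of injections, without naming a visit. This stands as a limit on the claim: later values of these measures are not shut out of the report. It does not repair the instruction. An over-time summary with no named visits or baseline is not the stated endpoint, and the one sentence that names the weeks names the wrong measure.

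On the cohort, the reply is that the plan sets up no formal contrast of Month 12 with Week 64. The study is descriptive and has no formal hypothesis. Each result is a within-patient change from baseline, n is reported, and only continuing patients can contribute on-treatment data at Weeks 64–104. Leaving for an expanded access program depends on the country and need not reflect poor response. All of this stands. What remains is that the 3.3 visit-window display puts the time points in sequence without a matched cohort.

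A reader might infer that the extended-dosing objective goes unanswered, or that no evidence of durability will exist. The document does not support that. TG at Weeks 64–104 is correctly planned in 3.3.2 from both baselines. Patients from the volanesorsen arms of the index studies entered after 12 months (CS6) or 6 months (CS16) on drug (Section 3.4.1.2), so their Month 3–12 changes from the Index Study Baseline already describe extended dosing. A reader might also infer that selection will flatter the later results by some definite amount. That would require response-dependent continuation, which the document does not show.

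**Conclusion.** The analyte error is certain on the text. As written, Sections 3.3.6 and 3.3.7 specify no change from baseline at Weeks 64–104 for 8 of the 9 measures in Section 1.4. It is an error in an operative instruction and should be corrected.

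The cohort gap is real but of unknown size. Reading Month 12 (FAS, possibly with off-treatment values) against Week 64 (extension patients) can mix selection with drug effect. Under the stated assumptions the shift is (1 − f) × D: 1 to 15 points for f from 0.5 to 0.9 and D from 10 to 30, and 0 if continuers do not differ. These figures show what the shift depends on and do not estimate it. Restricting Weeks 64–104 to extension patients is not itself a fault. What is missing is their own Month 3–12 summary.

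**What to change.** 1. In the extended-period sentence of Sections 3.3.6 and 3.3.7, replace fasting TG with the section's own measures: the seven other lipids in 3.3.6 and total apoC-III in 3.3.7.
2. In Sections 3.3.2, 3.3.6 and 3.3.7, add Month 3, 6 and 12 rows for patients enrolled in the extended period, placed beside Weeks 64, 76, 90 and 104. Show n at each visit and the paired within-patient change from Month 12.

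The cost is SAP wording and a few extra table rows, with no new data. The extension cohort may be small, so its Month 3–12 values will be less precise than those of the FAS. Matching at entry removes the shift in composition between Month 12 and entry to the extension. It does not remove the effect of later drop-out: the paired changes still depend on who remains at each later visit, which is why n should be shown.
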